4.6.1 Withdrawal

CYP and or their parents/carers/legal guardians may withdraw from HORIZON at any time, without giving a reason why and without affecting their care in the CYPGS. This includes all forms of intervention that may be offered by the CYPGS. Specifically, CYP may withdraw from HORIZON without affecting consideration of GnRHa and inclusion in PATHWAYS TRIAL.

If a CYP chooses to withdraw, they will be asked whether they assent/consent to their parent continuing to participate in HORIZON. Missing data at individual waves will not in itself constitute withdrawal unless the participant has explicitly so indicated.

A withdrawal form must be completed for each participant (CYP and/or parent) choosing to withdraw. A withdrawal form must be completed in the event of CYP death.

4.6.2 Change of parent

It will be possible for a new parent/ caregiver/ legal guardian to complete informant reports in the event that a parent/ caregiver/ legal guardian no longer wishes to participate or in the event of their death.

Should the informant change, a change of parent form will be completed, and separate consent will be obtained from the new informant. A withdrawal form will only be completed for the informant when consent for both parent and CYP is formally withdrawn.

4.7 Measures to promote participant retention

Honorarium: CYP and parent/carer/legal guardian completing informant measures will each receive shop vouchers worth £20 for each data collection episode, regardless of whether they have completed the assessment measures independently or with researcher support.

Researchers will send a newsletter to HORIZON participants at a minimum of twice annually. This will include news about the study and will provide an opportunity for participants to share their own news and accomplishments, if they wish.

4.8 DEVELOPMENT OF AN INTERVIEW-BASED NOVEL OUTCOME MEASURE FOCUSING ON YOUNG PEOPLE'S GOALS FROM THERAPY

We will co-develop with our advisory boards, as well as CYP attending the CYPGS and their parents/carers/legal guardians a new, bespoke interview outcome measure. This will be undertaken in year 1 of the study. Our previous focus groups with CYP and parents/carers/legal guardians from the Youth Advisory Forum highlighted the diversity of desired outcomes from gender-affirming care, a finding supported by clinicians' experiences in the Gender Service. Hence, we include a wide range of outcome measures to ensure comprehensive coverage. However, within the population of CYP experiencing gender incongruence, there is currently a poor understanding of which outcomes they wish to be altered through gender-affirming care. When this uncertainty is coupled with the lack of high-quality evidence for a range of therapeutic outcomes for young people, it limits the clinicians' ability to provide targeted information to assist decision-making. To address the question of individual preferences, we will ask CYP and their parents/carers/legal guardians to provide relative weightings for each of the beneficial and negative outcomes identified.

Development

The development phase will commence with a rapid literature review to identify a full set of items for consideration and response categories. (a) Specific consideration will be given to those that have been used in previous studies of gender incongruence (b) coverage of all domains identified by CYP and their parents/carers/legal guardians are important (c) items and response categories that can be objectified, e.g., with frequencies of occurrence or other anchor points and (d) items/response categories that are appropriate for the full age range of the study population, which will be 12-18 years at endpoint.

Following the review, response categories/domains and anchor points will be selected in consultation focus groups with our young adult and parent Advisory Boards, gender care health professionals and CYP without gender incongruence drawn from the general population. Two parallel versions (CYP and parent) will be evaluated by these groups for face and content validity of the items, clarity of probes, appropriateness of anchor points and also to establish any domains/items not highlighted in the literature.

Field Testing

Field testing of the pilot interview will be undertaken among: CYP attending the CYPGS but not considered eligible for the PATHWAYS Trial; CYP not seeking GnRHa through puberty and are no longer eligible for puberty suppression; CYP who have already received GnRHa. We will recruit 75 CYP-parent dyads to complete two independent interviews, no more than one month apart. These interviews will be offered online or in person and will be audio-recorded and re-rated by a second researcher. The interview topic guide will include questions related to the core domains assessed in the KIDSCREEN-52, as well as other domains identified in the literature and by the young adult and parent Advisory Boards.

On the first interview occasion, participants will also be asked to complete key study questionnaire outcome measures (KIDSCREEN, RCADS, BIS-GS, UGDS-GS, CBC-L/YSR). This will provide

a psychometric dataset for test-retest and inter-rater reliability, CYP-parent agreement and convergent and discriminant validity.

Finally, using an online questionnaire of all domains, CYP and parents/carers/legal guardians will be asked to order a complete list of the domains to represent their personal priorities. For younger CYP and CYP/parents/carers/legal guardians with learning difficulties, the task can be supported by a researcher. This task will be completed on the first interview occasion alongside the key study questionnaire outcomes measures.

A purposive sample of 70 CYP-parent dyads will be invited to participate in a third interview 6-months after their baseline interview, in order to test the novel outcome measure's sensitivity to change.

Initial interviews and questionnaire completion will take 90-120 minutes and re-test interviews 60 minutes. Participants will be reimbursed £30 and £20 respectively for each session.

Please refer to Annex 2 (table 5) for the novel outcome measure schedule of events.

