8.7 ANALYSIS OF NOVEL OUTCOME MEASURE

The primary aim is to establish the psychometric properties of the novel measure. The most important characteristics are inter-rater and test-retest reliability, but we also want to understand its convergent validity with the primary outcome measure, KIDSCREEN-10 and other outcome measures of mental health and behaviour, gender identity and body dysphoria. All of these established measures generate continuous scores.

Individual items in the novel measure will a priori map to measure domains, e.g., gender identity, emotions, family life, etc. Each domain will generate an individual score which will form a component of the total score. Domain will be ordinally or continuously distributed, and the total score will be continuous.

Inter-rater and test-retest reliability using intre-clss correlations (ICCs) will focus on the total score; while these characteristics of domain scores will be extracted, it is recognised that there will be lower levels of agreement. Similarly, associations to other outcome measures will be evaluated with ICCs, with a priori expectations of relative convergence amongst measures tapping overlapping concepts and experiences.

The measure will be considered a valid primary outcome for gender incongruence if inter-rate and test-retest reliability are both 0.7.

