1=protocol adherence; 2= personal priorities and quality of life; 3= gender; 4=mental health; 5= neurodevelopmental difference; 6=physical health; 7=adverse events **Information source:**

R=researcher-completed; SQ=self-reported questionnaire; PQ=parent-reported questionnaire; PQ**= parent reported questionnaire at baseline only; D=direct observation/examination

^{*} If a participant turns 16 during the study, consent must be sought

Table 4: Schedule of Events for information collected by clinicians/researchers

Event/Form	Domain, information source (see legend)	Baseline	Month 12	Month 24	Annual Follow Up	Ongoing*	Estimated completion time (minutes)
Registration form & consent	R (1)	X					5
Eligibility	R (1)	X					10
Medical history	D (6)	X					150
Demographic data	D (1)	X					2
Status form	R (1)		X	X	X		1
Withdrawal form	R (1)					X	2

LEGEND

Domains:

1=protocol adherence; 2= personal priorities and quality of life; 3= gender; 4=mental health; 5= neurodevelopmental difference; 6=physical health; 7=adverse events **Information source:**

R=researcher-completed; SQ=self-reported questionnaire; PQ=parent-reported questionnaire; D=direct observation/examination;

^{*} If a participant turns 16 during the study, consent must be sought

Table 5: Schedule of Events for novel outcome measure

Event/Form	Domain, information source (see legend)	Baseline	Follow-up (within 1-month of baseline)	Follow-up (within 6-months of baseline)	Estimated completion time	
					(minutes)	
Informed consent/ assent	SQ, PQ	X			10	
Interview	D (2) (3) (4) (6)	X	X	X	60	
Personal treatment priorities	SQ, PQ (2)	X			5	
Quality of Life (KIDSCREEN-52)	SQ, PQ (2)	X			7	
Anxiety and depression symptoms (RCADS-25)	SQ, PQ (4) (7)	X			5	
Gender dysphoria (UGDS-GS)	SQ (3)	X			3	
Body image/ dysphoria (BIS-GS)	SQ (3)	X			3	
Emotional & Behavioural Problems (CBCL, YSR)	SQ, PQ (4)	X			15	

Legend

Domains:

1=protocol adherence; 2= personal priorities and quality of life; 3= gender; 4=mental health; 5= neurodevelopmental difference; 6=physical health; 7=adverse events

Information source:

R=researcher-completed; SQ=self-reported questionnaire; PQ=parent-reported questionnaire; D=direct observation/examination

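### The 6-month interview is meant to test the new measure's sensitivity to change, but no external indicator of change is scheduled at that session

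*Protocol*

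**What the plan says.** Section 4.8 (Field Testing) sets up two pieces of work. The first is for reliability: "We will recruit 75 CYP-parent dyads to complete two independent interviews, no more than one month apart". The second, a test of sensitivity to change, was added in protocol version 1.1. For it, 70 purposively chosen dyads are asked to "participate in a third interview 6-months after their baseline interview, in order to test the novel outcome" instrument in that respect.

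The established questionnaires are tied to one session: "On the first interview occasion, participants will also be asked to complete key study questionnaire outcome measures", namely KIDSCREEN, RCADS, BIS-GS, UGDS-GS and CBCL/YSR. Their stated use is to provide "a psychometric dataset for test-retest and inter-rater reliability, CYP-parent agreement and convergent and discriminant validity"; change is not on that list. The ranking of personal priorities is tied to the same session: "This task will be completed on the first interview occasion alongside the key study questionnaire outcomes measures".

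Annex 2 Table 5 agrees with the text. Only the interview row is marked at all three occasions; the priorities task and all five questionnaires are marked at baseline only. The table heads the third occasion "Follow-up (within 6-months of baseline", whereas the text puts it 6 months after the first interview.

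Section 8.7 plans inter-rater reliability, test-retest reliability and "convergent validity with the primary outcome measure", and sets a threshold of 0.7 for the two reliabilities.

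**The concern.** Sensitivity to change means that a score moves when the person's condition has moved and stays put when it has not. Testing it requires some source other than the score itself that says who changed: a second reading on an established scale, a global rating of change, or a known event. Under Table 5 the new interview is the only thing measured at the third session, so its change has nothing planned and dated to the same point to be set against.

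Secondary objective 2 is to develop this measure, and section 8.7 contemplates its use as a primary outcome for gender incongruence. Evidence on responsiveness is what a later user would need before adopting it as an endpoint. A 6-month reading that was not taken cannot be recovered afterwards. A statistical analysis plan can define how change is analysed, but it cannot supply data that the schedule does not collect.

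**Working it through.** The protocol gives no power or precision figure for the third interview, so there is none to reproduce. The check is of the schedule, followed by illustrations whose assumptions are mine.

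**1. Schedule (Annex 2, Table 5)**

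| Item | First interview | Within 1 month | 6 months | Minutes |
|---|---|---|---|---|
| Interview | yes | yes | yes | 60 |
| Personal priorities | yes | – | – | 5 |
| KIDSCREEN-52 | yes | – | – | 7 |
| RCADS-25 | yes | – | – | 5 |
| UGDS-GS | yes | – | – | 3 |
| BIS-GS | yes | – | – | 3 |
| CBCL/YSR | yes | – | – | 15 |

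Comparators with a 6-month value under this schedule: 0 of 5. No global rating of change is listed as a form.

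**2. Can the annual waves stand in?** Participants in this sub-study are drawn from HORIZON (section 3.3), and Table 1 repeats all five instruments every year. Section 3.4.1 dates those waves from the first CYPGS assessment, with a window from 6 weeks before to 5 months after the anniversary: 42/30.44 + 5 ≈ 6.4 months wide. Nothing ties either interview to that calendar. Some dyads will have an annual value near the third interview, and some will not.

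**3. What the new score can show alone** (assuming 70 complete dyads, two-sided 5%)

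- Smallest detectable standardised response mean (SRM), (1.96 + z_power)/√70: 2.80/8.37 = 0.33 at 80% power; 3.24/8.37 = 0.39 at 90%.
- 95% half-width around an SRM near zero: 1.96/8.37 = 0.23.

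So movement of the score can be tested. Its cause is another matter.

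**4. Why a flat score is ambiguous.** Simulation with 2,000 runs, n = 70, reliability 0.7 for both measures, and true change either none or a mean of 0.5 SD (SD of change 0.7):

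| Situation | SRM, new score | SRM, repeated comparator |
|---|---|---|
| No true change, sensitive measure | −0.01 | 0.00 |
| True change 0.5 SD, insensitive measure | 0.00 | 0.44 |
| True change 0.5 SD, sensitive measure | 0.44 | 0.44 |

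The 0.44 can be checked by hand. The error variance of a change score is 2 × 0.3/0.7 = 0.857, and 0.5/√(0.49 + 0.857) = 0.43. The first two rows look the same on the new score by construction: in both, its change is pure error. Only the comparator column separates them.

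**5. Precision if the comparators were repeated.** Fisher z for an observed change-score correlation r, using atanh(r) ± 1.96/√67 (= ±0.239):

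- r = 0.30: 0.310 ± 0.239, giving 0.07 to 0.50
- r = 0.40: 0.18 to 0.58
- r = 0.50: 0.30 to 0.66

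**6. Added time.** 7 + 5 + 3 + 3 = 18 minutes; with CBCL/YSR, 18 + 15 = 33 minutes. On a 60-minute session that makes 78 or 93 minutes (30% or 55% more). Section 4.8 accepts 90–120 minutes for the first session.

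**The case against.** The case on the other side has real content, and it limits how far the point can go.

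- **Second readings will exist.** A reader of Table 5 alone might infer that no established scale is ever measured again. That is wrong: HORIZON repeats all five every year, and the field-test groups are largely outside TRIAL and so stay on that schedule. What is missing is a reading dated to the third interview.
- **Routine records.** The sub-study consent (section 3.3) covers routine clinical outcomes and records, a possible outside indicator of change. It stands as a possibility only, since no instrument or time point is named.
- **Retest and re-rating.** The one-month retest and second-rater scoring estimate measurement error, so 6-month movement can be judged against noise, and parallel child and parent versions allow a check on concordance. This goes a good way for a moving score. It does not resolve a flat one, nor does it show that movement is change in the intended construct.
- **Purposive sampling.** The 70 might be chosen because change is expected. No selection basis is given, and none of the field-test groups is tied to an event expected to produce change. If the 70 come from the 75, 70/75 = 93% are invited, which leaves little room to select.
- **Interview content is still to be developed,** so the interview may yet include a change question. The documents neither promise nor exclude it.
- **Limited consequence.** Section 8.7 rests the validity decision on reliability alone, and no primary objective or cohort result depends on the third interview.

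**Conclusion.** The point holds in a limited form. Text and table agree that no external indicator of change is scheduled at the session whose only stated purpose is to test sensitivity to change. The annual waves give a partial anchor by chance, and routine records an unspecified one. A flat 6-month score therefore cannot be attributed to stable participants rather than to an insensitive measure, and a moving score cannot be checked against same-time change on an established scale.

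The stronger inference, that the third interview cannot serve its purpose at all, is not supported. Change can be tested against retest error, and with 70 complete dyads an SRM of about 0.33 is detectable at 80% power. This is a low-cost improvement to one secondary objective, not a threat to the cohort's main results.

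The schedule finding needs no assumptions. The precision figures assume that all 70 invited dyads complete, and the correlations are illustrative. The simulation also assumes reliability of 0.7 and the stated amounts of true change. Fewer completers would widen the intervals.

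**What to change.** In section 4.8 and Annex 2 Table 5, mark KIDSCREEN-52 (which contains the KIDSCREEN-10 items), RCADS-25, UGDS-GS and BIS-GS at the 6-month interview as well, with CBCL/YSR optional. Preferably add a single global rating of change since the first interview, one from the young person and one from the parent. State that change in the new score will be related to change in these measures; the detail can go in the statistical analysis plan. In the same amendment, reconcile the two descriptions of the third occasion, since an interview held at any time up to 6 months is not the same as one held at 6 months.

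The cost is about 18 minutes more per third session (33 with CBCL/YSR) on top of 60, plus a few moments for the global rating, and possibly a larger voucher than the £20 set for re-test interviews. The questionnaires are already in use in the study and no extra visit is needed, though any researcher-supported completion would take staff time. The change has to be in place before the 6-month interviews start.

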5. DATA MANAGEMENT

5.1 DATA MANAGEMENT

The Medrio EDC system dataset, which includes data from the Medrio ePRO module, forms the dataset for the study. The CI will act as custodian for the trial data.

5.1.1 Medrio EDC

A web based electronic data capture (EDC) system will be created in collaboration with the CI and trial analyst(s), using the Medrio system. This will be maintained by the King's Clinical Trials Unit (KCTU) and Medrio for the duration of the project. It will be hosted on secure servers by Medrio in the EU.

Source data will be entered in the EDC by authorised site staff, typically within 7 days of data collection by going to www.ctu.co.uk and clicking the link to Medrio EDCs. A full audit trail of data entry and any subsequent changes will be automatically date and time stamped, alongside information about the user making the entry/changes.

SDWs will be supplied to all recruiting sites by the TM. These will be prepared after the database specification is finalised and database testing is complete. Participating Sites will complete source data location lists defining the source data at their site.

The CI or delegate (e.g., Trial Manager) will request email usernames and passwords from KCTU for new staff members joining the study and will request access removal when staff members leave the project. EDC access is strictly restricted through user-specific passwords to the authorised research team members. It is a legal requirement that passwords to the EDC are not shared, and that only those authorised access the EDC.

Site staff experiencing issues with the EDC system should contact the CI or delegate (e.g., Trial Manager). Medrio training videos are available at www.ctu.co.uk under 'Resources – Events & Training' tab.

5.1.2 Medrio eConsent

The web based Medrio EDC system will include eConsent (electronic consent).

It is the responsibility of the recruiting site staff to ensure participant identification is verified and documented, and that the participant has had the opportunity to have any questions answered. Recruiting site staff should ensure a copy of the completed consent is provided to the participant and that there is written documentation to evidence this. A copy should also be saved in the Investigator Site File (ISF).

Completing eConsent

Authorised staff will log in to their Medrio EDC account and 'Add' the participant. There are 2 options for eConsent activation & completion as described below:

1. Remote Completion by Participant (e.g., at home completion):

For 'Remote' completion (e.g., completion on a computer/smartphone/tablet at home), staff member will enter the participant email address when adding the participant in the EDC. A 'Set up Profile' email will be automatically sent to the participant with a link to set up their Medrio Profile and create a password.

A 'Consent' email will be automatically sent alongside this with a link to their Medrio Profile containing the eConsent document for review and signature.

Where multiple signatures are required (e.g., Parent & Child), the staff member will need to ACTIVATE REMOTE eConsent within the EDC. The participants will receive a notification each with a link to their Medrio Profile containing the eConsent document for review and signature.

2. In Clinic completion by Participant:

Authorised staff can LAUNCH the eConsent document within the EDC and hand the computer/smartphone/tablet to the participant for completion at the clinic visit. Where multiple signatures are required (e.g., Parent & Child), In Clinic completion is not possible.

eConsent co-signing by Staff and completing Registration

Once participant signature is complete, an authorised staff member will log in to their Medrio EDC account to review correct completion by the participant, co-sign the eConsent and provide a copy to the participant.

Next, the staff member can complete the participant Registration in the EDC so that remaining data can be completed as necessary.

5.1.3 Medrio ePRO

The web based Medrio EDC system will include ePRO (electronic Patient Reported Outcomes).

Participant Self Report Data (ePRO) Oversight

It is the responsibility of the site staff to ensure ePRO forms are complete at each timepoint for all participants (including where completion is In-Clinic, Remote or on Paper), as a high amount of missing data can render the study uninterpretable.

Authorised staff can check ePRO form completion by logging into their Medrio EDC account. Site staff will be responsible for following up participants who have not completed their ePRO forms before the end of each scheduled timepoint.

Participant Withdrawal

Where a participant wishes to withdraw from all further data collection for the study, staff should complete the EDC withdrawal form as soon as possible (i.e., on the same day) to ensure the participant does not receive further notifications via the automatic ePRO scheduler.

Data Entry Guidance for Participant Self Report Data (ePRO)

No data will be entered via ePRO unless a participant has signed a consent form to participate in the trial.

There are 3 options for ePRO data entry described below:

1. In Clinic Data Entry by Participant

After participant registration in the EDC, authorised staff can launch the relevant ePRO form(s) on a computer/smartphone/tablet and hand this to the participant for completion at the clinic visit.

2. Remote Data Entry by Participant (e.g., at home completion):

For 'Remote' ePRO (e.g., completion on a computer/smartphone/tablet at home), when the participant is registered in the EDC and their email address is entered by the authorised staff member, the participant will receive a 'Set Up Profile' notification email. The participant can follow the link in the email to set up their Medrio Profile and create a password. A notification containing a link to the required ePRO form(s) will be sent to participants as per the pre-defined schedule. The participant will log in to their Medrio Profile, using their email address and password, to complete the active ePRO form(s) for that timepoint.

3. Data Entry by Site Staff if collected on Paper first:

If any ePRO forms are completed on paper instead, data entry users will transcribe these data into the EDC (as with any other non-ePRO forms) as soon as possible.

